7.4. Case Report Forms

All assessments and observations throughout the investigation must be carefully recorded in an electronic CRF (eCRF). Details about data capture can be found in section 10.1

Forms that need subject signature will be present in paper format (pCRF).

Any correction in the pCRF must be clearly signed and dated by authorised site personnel. The entry corrected must be crossed out so that the entry is still legible.

Example 1:

20/01-11 [name]
07 JAN 2011
Day Month Year
Ex. AUG

Example 2:

No Yes
20/01-11 [name]

Figure 2 Two examples of how to make corrections in the pCRF

7.5. Concomitant treatment

Concomitant treatment, including relevant medication, will be registered in the CRF.

7.6. Supplementary materials and equipment (if applicable)

The Sponsor will provide the Principal Investigator, or delegate with supplementary materials for this investigation. Supplementary materials would be:

- Computer or Iphone with access to eCRFs
- Nurse kits including disposal bags, gloves, gauze, disinfection gel etc.

8. Monitoring and source data verification

All data collected will be directly entered into the eCRF and the EDC system will via edit checks ensure that all fields are completed in the eCRF.

The Informed Consent Forms and (S)AE/ADE will be 100% monitored for timely completeness. eCRF's will be remotely monitored with regards to completeness.

Only the investigator, delegated site personnel and the sponsor representatives will have access to all the eCRFs. The subject will have access to his/her own CRF.

8.1. Remote monitoring

Remote or centralized monitoring is a remote evaluation carried out by sponsor personnel or representatives (e.g., data management personnel, statisticians, or clinical monitors) at a location other than the site(s) at which the clinical investigation is being conducted. Remote monitoring processes can provide many of the capabilities of on-site monitoring as well as additional capabilities.

In addition to onsite monitoring visits, remote monitoring of the data entered in the eCRF system could be used to achieve the following:

- Conduct activities such as: standard checks of range, consistency, and completeness of data and checks for unusual distribution of data, such as too little variance)

- Special attention will be given in case of frequent data anomalies or errors, protocol violations or excessive drop outs.
- Augment on-site monitoring by performing monitoring activities that can only be accomplished using centralized processes (e.g., statistical analyses to identify data trends not easily detected by on-site monitoring)
- Monitor data quality through routine review of submitted data in real-time to identify missing data, inconsistent data, data outliers, and potential protocol deviations that may be indicative of systemic and/or significant errors in data collection and reporting at the site
- Verify source data remotely, provided that both source data and CRFs can be accessed remotely
- Conduct aggregate statistical analyses of study data to identify subject data that are outliers relative to others and to evaluate individual subject data for plausibility and completeness
- Conduct analyses of site characteristics, performance metrics (e.g., high screen failure rates, high frequency of eligibility violations, and delays in reporting data), and clinical data to identify early on corrective actions needed for characteristics correlated with poor performance or noncompliance

8.2. Other methods for data quality assurance

The sponsor, sponsor's representative and/or investigational sites may be inspected by competent authorities or their representatives and likewise may be audited per Coloplast's internal quality audit plan and procedures. The investigator allows access to source data, medical records and other relevant documents for this study both for monitoring, audit and/or inspections from the Ethics Committee and competent authorities.

9. Statistical considerations

9.1. Statistical design, method and analytical procedures

Endpoints and assessments

All baseline assessments, endpoints and other measurements will be reported by descriptive statistics and/or listed.

Analysis populations

Intention to Treat (ITT), Safety and Per Protocol (PP) populations will be defined at a formal data review meeting just before database lock. As a minimum, the clinical manager and the statistician will be involved in the classification of subjects.

The Safety population (basis for the AE summary) will constitute subjects with valid informed consent.

The ITT population (Full analysis set) will constitute all subjects, with valid informed consent, who have been exposed to at least one product and furthermore, with information recorded on at least one endpoint (non-missing).

No formal PP population is planned. However, if additional explorative analyses are deemed necessary, a PP population will be established, based on a subset of the ITT population.

Individual endpoints/data points may be excluded from analysis, even though the corresponding subject belongs to the ITT population. This situation could arise due to protocol violations, where, at one visit, the primary endpoint could be affected, but same effect did not occur at the following visit.

All analysis will be based upon the ITT population and AEs will be summarized based on the safety population.

Any exclusion of subjects or data points from any of the populations must be documented.

Descriptive statistics for continuous variables are presented with N, Mean, SD (standard deviation), Median, Min and Max), where N denotes the number of subjects contributing with non-missing data. For discrete variables, descriptive statistics are presented with N and percentage, where percentage is based on the total number of subjects/observations with non-missing data.

A significance level of alpha equal to 0.05 (two-sided) is applied.

All endpoints will be analyzed by an exact test in the binomial distribution (proportion is equal to 50%), where the frequency of success or will estimated with 95% confidence limits.

The two highest or best categories in questions obtained from a 5-point ordinal scale is defined as a success. Likewise, the answer yes, is defined a success, obtained from questions with a yes/no categorical option.

In favor of a claim, the lower 95% confidence limit must be above 50%.

Other summaries and analyses can be made, if relevant.

All statistical analyses and summaries are made with SAS version 9.4 (SAS Institute Inc., Cary, NC)

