6.4. Point of enrolment

A subject is considered enrolled in the investigation when the written informed consent is obtained. The expected duration for each subject is described in section 4.1.

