7.1.1. Visits

Visit 0 (Inclusion visit)

If a potential subject is interested in participating after the first contact, a visit (visit 0) will be arranged at subject's home or at a clinic or at Coloplast, if subjects prefer not to have visits in own home, in a room reserved to ensure privacy and quiet surroundings. When arranging the visit, it will be ensured, that the subject has received the Subject Information Form prior to the visit. The subjects will receive both written and verbal information to ensure that the subject understands what was read and explained and can freely agree to participate in the investigation. The subject will, beforehand, also be informed about the possibility of bringing a companion to Visit 0 and to any possible subsequent visits. During the visit the principal Investigator, or delegate, will provide oral information about the investigation based on the Subject Information Form. The subject has the right to wait before deciding on participation.

If/when subjects decide to participate, they will be asked to sign the Informed Consent Signature Form. If a subject so desires, and it is certain that it is understood what the investigation entails, and the relevant form has been signed, the subjects are considered enrolled in the investigation. Enrolled subjects that are deemed eligible per the inclusion/exclusion criteria are allocated a subject number. Visit 0 and visit 1 can be combined.

Visits 1 (V1)

During visit 1, part 1 of the questionnaire Table 1 (demographic questions) will be completed by the Principal Investigator, or delegate. The subject will be trained in the use of the test product per IFU. The subjects are instructed to continue their everyday life and change test product whenever they feel the need to.

Visits 2 (V2)

During visit 2, the Principal Investigator, or delegate will ensure part 2 of the questionnaire [Table 2](#) will be completed by subjects. Potential (S)AE's will be captured by the Principal Investigator, or delegate. Hereafter termination If appropriate, subjects may be interviewed regarding use of the test product by a Coloplast representative at V2, otherwise an alternative time for interview may be scheduled.

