16.2. Adverse device effect

An adverse event, which is related to the use of the investigational medical device, is an adverse device effect, and should be marked as related or possibly related on the adverse event form.

The definition of an adverse device effect includes any event resulting from insufficiencies or inadequacies in the instruction for use, e.g. mounting of the medical device, or any malfunction of the medical device, as well as any event resulting from use error or from intentional misuse of the device.

The anticipated adverse device effects are well known adverse events from the use of the investigational device.

Table 3 Anticipated adverse device effects and their likely incidence rates

ANTICIPATED ADE	INCIDENCE RATE
Skin irritation, intact skin (area covered by the product) [1]	3-25%
Allergic skin irritation [2]	< 1%

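### The Safety population is defined by consent alone, so adverse device effect percentages can be understated if any consented man never wears the device

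*Combined protocol and SAP*

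**What the plan says.** Section 9.1 sets out the analysis populations. For safety: "The Safety population (basis for the AE summary) will constitute subjects with valid informed consent". The section then assigns the sets to their uses: "All analysis will be based upon the ITT population and AEs will be summarized based on the safety population". The ITT set has two further conditions. It is limited to men "who have been exposed to at least one product", and they must also have at least one endpoint recorded. For discrete variables, the "percentage is based on the total number of subjects/observations with non-missing data".

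Section 6.4 fixes the start of participation: "A subject is considered enrolled in the investigation when the written informed consent is obtained". Section 7.1.1 places the eligibility decision among men who are already enrolled: "Enrolled subjects that are deemed eligible per the inclusion/exclusion criteria are allocated a subject number". Inclusion criterion 8 in Section 6.1 concerns whether the product fits. Training in its use takes place at V1, which may or may not be combined with V0. Under Sections 6.3 and 9.2, men who leave are not replaced.

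Section 16.2 defines an adverse device effect as an adverse event related to use of the device. Table 3 in that section anticipates skin irritation in 3-25%.

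**The concern.** Exposure is required for the efficacy-type analysis but not for the safety analysis. Between consent and first use a man can be found ineligible, fail the fit criterion, or change his mind. Section 7.1.1 has adverse events captured at V2, and Section 6.3 provides no follow-up for withdrawn men without an event. A man who leaves before first use would therefore usually add one to the denominator and nothing to the numerator.

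For device effects the error can go only one way, because a man who has not used the device cannot have an effect of using it. The percentage then describes consented men rather than wearers, and it makes the device look slightly safer than it was among those who wore it. With 20 men, each unexposed man carries visible weight.

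**Working it through.** **Inputs.** Twenty men are to be enrolled (Section 6) and enrolment is at consent (Section 6.4), so the consent-based Safety set has N = 20. Let k be the number of consented men who never wear the device. The documents give no value for k; the range 0 to 5 is an assumption. The plan reports no adverse event rate or safety calculation, so there is no figure of its own to reproduce.

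**Formula.** If x men have a device effect, the rate among wearers is x/(20 − k) and the reported rate is x/20. Hence:

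reported rate = rate among wearers × (20 − k)/20, a relative understatement of k/20.

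**Results for an illustrative x = 4**, reported as 4/20 = 20.0% whatever the value of k:

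| Assumed k | Exposed men | Factor (20 − k)/20 | Rate among wearers | Relative understatement |
|---|---|---|---|---|
| 0 | 20 | 1.00 | 4/20 = 20.0% | none |
| 1 | 19 | 0.95 | 4/19 = 21.1% | 5% |
| 2 | 18 | 0.90 | 4/18 = 22.2% | 10% |
| 3 | 17 | 0.85 | 4/17 = 23.5% | 15% |
| 4 | 16 | 0.80 | 4/16 = 25.0% | 20% |
| 5 | 15 | 0.75 | 4/15 = 26.7% | 25% |

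**Precision.** The exact (Clopper-Pearson) 95% interval for 4/20 is 5.7% to 43.7%. With no events, the exact upper 95% limit is 16.8% on 20 men, 19.5% on 17 (k = 3) and 21.8% on 15 (k = 5).

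**All adverse events.** Section 16.1 counts events whether or not they are related to the device, so an unexposed man can have one. Take k = 1 with four events among 19 wearers. If the unexposed man has no event, 21.1% is reported as 20.0%. If he has an unrelated event, it is reported as (4 + 1)/20 = 25.0%, which is higher than the rate among wearers. The direction is therefore certain for device effects only.

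**The case against.** The strongest reply is that unexposed men may be few or absent. Under Section 6.2 the criteria are gone through by telephone before the subject information is sent, and men who fail are entered in the screening log without having consented. V0 and V1 can be combined, and Table 1 gives them a single column, so the interval between consent and first use may be short. Only eligible men receive a subject number, the populations are settled at a data review meeting before database lock, and percentages use non-missing data. Any of these might in practice keep an ineligible man out of the denominator. This stands as a limit on the likely size of k, and it makes withdrawal before first use the firmer example. It does not remove the point: none of these provisions states an exposure condition, and a classification made just before lock is weaker than a rule fixed in advance.

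A consent-based set also has a proper purpose, since it leaves out no event after enrolment. That stands too, and the fix keeps it.

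A reader might infer three stronger things that the documents do not support:

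- That the rates will be diluted. This requires at least one unexposed man, and nothing in the documents says there will be one.
- That every adverse event rate is understated. Section 16.1 allows unrelated events in unexposed men.
- That the observed rates would be misjudged against Table 3. For example, 5/19 = 26.3% lies above the anticipated 3-25%, while 5/20 = 25.0% lies within it. But no such comparison is planned, and Table 3 does not state its denominator.

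**Conclusion.** The point holds in conditional form and is minor. As written, Section 9.1 gives the wrong denominator for adverse device effects whenever a consented man is never exposed. The understatement is k/20 in relative terms: 5% for one such man, 20% for four, none for zero. This rests on 20 consented men in total and on an assumed k. For one or two men the shift (20.0% against 21.1% or 22.2% in the illustration) is small beside the sampling error at this sample size.

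No pass criterion depends on it. Section 9.4 concerns claims only, and the comfort endpoint and the claims are analysed on the ITT set, which already requires exposure.

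**What to change.** In Section 9.1, define the Safety population as all consented subjects exposed to at least one test product, whether or not they have endpoint data. Use it as the denominator for adverse event and adverse device effect percentages. List separately any adverse event in consented, unexposed men, so that no event is lost, and report how many such men there were.

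The ITT set should not be used as a substitute. It also requires endpoint data, which are collected only at V2, so it could drop a man who wore the device and stopped early because of an adverse event.

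The cost is a sentence or two in Section 9.1. Exposure can be established from the device accountability records in Section 13, which cover the number of devices used and the subject's identification. The one downside is that the rates may look slightly less favourable.

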9.2. Sample size

Due to the conceptual nature of this trial no formal sample size calculation has been performed. It is assumed that 20 subjects will be adequate for evaluating the comfortability of the test product.

We strive to include subjects representing most possible age groups in the study.

Due to the exploratory nature of the study, drop-out subjects will not be replaced.

9.3. Level of significance and power

If a statistical analysis is performed a significance level of 5% will be applied. As this is an exploratory study no power has been applied.

9.4. Pass/fail criteria

The study is conducted as a proof of concept study.

Pass criteria is defined as: In favor of a claim, the lower 95% confidence limit must be above 50%.

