3.2. Hypotheses

[figure not shown]
There is no formal hypotheses associated to this study.

The study will provide valuable insight into the use of the device in an everyday life setting.

4. Design of the clinical investigation

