4.2.1. Primary endpoint

Primary endpoint:

- Frequency of success in support of "comfortable"

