4.2.2. Secondary endpoints

Secondary endpoints:

- Frequency of success in support of various commercial claims

Please see [Table 2](#) for a detailed listing of all endpoints

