At completion of the investigation sponsor is responsible for writing the clinical investigation report. The report is retained on file. The report contains a critical evaluation of all data, which have been collected during the investigation. The report describes the methodology and design and a data analysis, including statistical preparation and conclusion.

Sponsor and coordinating investigator must sign the final version of the clinical investigation report or an affidavit, indicating their agreement with the contents. If no coordinating investigator is appointed, then the signatures of the principal investigator(s) should be obtained.

The clinical investigation report must be submitted to EC and regulatory authorities, if the investigation has been subject to approval from regulatory authorities.

19. Publication policy

Coloplast, sponsor, is referring to the internal document 'Clinical Publication Policy' that will be available for internal and external persons involved in the publication process.

The investigation will be registered on a public accessible database, e.g. www.ClinicalTrial.gov, before recruitment of the first subject. The results of the investigation, positive as well as inconclusive and negative will be published in the same public accessible database. The subjects' identity will remain confidential. Publication of results in the database will be conducted per the law of personal data protection and will be initiated as soon as scientifically acceptable, however, within one year after the last subject has completed the investigation. Data from the investigation is considered confidential until it is published per the conditions of this CIP and the 'Clinical Publication Policy'. Sponsor may publish anonymous single subject case stories at any time during and after the investigation. The identification of the subjects must not be possible. Sponsor reserves the right to use the data (published and unpublished) for reimbursement or regulatory purposes.

20. Bibliography

[2]

[3] Clinical Investigation Device Label CP326, Doc. No: VV-0287510

[4] Instruction for Use CP326, Doc No: VV-0287489

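### Does section 9.4 need to say that comfort alone decides the study's pass, and that the 21 secondary claims are unadjusted for multiplicity?

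*Combined protocol and SAP*

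**What the plan says.** Section 9.4 opens with "The study is conducted as a proof of concept study" and then gives its only criterion: "Pass criteria is defined as: In favor of a claim, the lower 95% confidence limit must be above 50" per cent. Section 9.1 states the same criterion and applies one method throughout: "All endpoints will be analyzed by an exact test in the binomial distribution (proportion is equal to 50" per cent), at a two-sided 0.05 level with 95% limits. A success is one of the two best categories of a five-point item, or a yes.

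Sections 3.1 and 4.2.1 make comfort the only primary objective and endpoint. Section 4.2.2 describes the secondary endpoints as "Frequency of success in support of various commercial claims" and refers to Table 2 for the list. The sample-size remark in section 9.2 concerns comfort: "It is assumed that 20 subjects will be adequate for evaluating the comfortability of the test product". Sections 9.2 and 9.3 call the study exploratory and give no power.

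Section 3.2 says "There is no formal hypotheses associated to this study". No section mentions multiplicity, a testing order or a study-level pass rule.

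**The concern.** A section headed pass/fail criteria, in a study described as a proof of concept, would be expected to say what makes the study pass. This one speaks only of a claim, and 22 claims qualify. It could be read as comfort deciding, as any one claim being enough, or as every claim being needed. If the reading were chosen after the results were known, the same data could be called a pass or a fail.

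The secondary results are also meant to support commercial claims, and the plan does not say that a favourable one is among 22 unadjusted tests. In addition, section 3.2 disclaims formal hypotheses while section 9.1 tests a 50% null, so the status of the tests looks unsettled.

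**Working it through.** **Inputs.** The rule is a lower 95% limit above 50% (sections 9.1 and 9.4). The test is exact binomial against 0.50 at two-sided 0.05 (section 9.1). The sample is 20 men, with drop-outs not replaced and no drop-out rate given (sections 6 and 9.2). Table 2 in section 7.3 has 17 five-point and 5 yes/no endpoints, so 22 in all: 1 primary and 21 secondary. The plan gives no power or calculated sample size to reproduce.

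**1. Cut-off for one claim.** The exact (Clopper-Pearson) lower limit for r successes out of n is the 0.025 quantile of Beta(r, n − r + 1).
- 14/20 gives 45.7%, which fails.
- 15/20 gives 50.9%, which passes.

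Section 9.1 does not name the interval method, but Wilson, Agresti-Coull, Jeffreys and Wald limits also give 15/20.

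**2. Error for one claim.** P(X ≥ 15 | 20, 0.5) = (15504 + 4845 + 1140 + 190 + 20 + 1) / 1048576 = 21700 / 1048576 = 0.0207, below the 0.025 allowed in the upper tail. With 19, 18 or 17 answers the cut-offs are 15, 14 and 13, and the errors are 0.96%, 1.54% and 2.45%. Each claim keeps its stated level.

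**3. At least one of 22 claims, all true rates 50%.**
- Independent answers: 1 − (1 − 0.0207)^22 = 0.369.
- Expected false passes: 22 × 0.0207 = 0.46, whatever the correlation.
- The same men answer every item, so independence is the upper end. Simulation with one shared latent factor gives about 30%, 24%, 19% and 12% at correlations 0.3, 0.5, 0.7 and 0.9. These correlations are assumed; the documents give none.

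**4. What an adjustment would cost.** Bonferroni over 22 claims allows 0.025 / 22 = 0.00114 per tail. P(X ≥ 17) = 1351 / 1048576 = 0.00129 is too large, and P(X ≥ 18) = 211 / 1048576 = 0.00020 is small enough, so the cut-off becomes 18/20. At an assumed true rate of 80%, the chance that a claim passes falls from 0.804 to 0.206. Expected supported claims fall from 22 × 0.804 = 17.7 to 22 × 0.206 = 4.5.

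**5. What a clarifying sentence would change.** Suppose section 9.4 said that comfort carries the main conclusion and that the other 21 claims are unadjusted. The cut-off would stay at 15/20, and each claim's numerator, denominator, estimate, limits and verdict would be the same as under the present text.

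**The case for a change.** The strongest case for a change is that exploratory status excuses unadjusted tests only when they are declared. These results are meant for use: section 3.1 names commercial claims, and section 19 reserves the data for reimbursement or regulatory purposes. If comfort truly stood at 50% and the other 21 items at 80% (assumed rates), a comfort-only rule would pass the study 2.1% of the time, an any-claim rule 98% to 100%, and an all-claims rule 0% to 2%. A few sentences would remove that spread at no cost in subjects.

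Part of this stands. Section 9.4 does not state comfort's role, no section says that the tests are unadjusted, and section 3.2 does not match section 9.1.

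The rest does not carry through:
- A rule worded for a single claim gives no support to an all-claims reading.
- The 98% to 100% figures are not claim-level errors, because a secondary claim that passes at a true 80% is a correct one.
- The plan attaches no consequence to a study-level pass. There is no go/no-go step, and the device is to be CE-marked before the study starts (sections 5.1 and 14.1).
- Selective reporting is already addressed. Section 9.1 has every endpoint described or listed, section 18 requires a critical evaluation of all data, and section 19 says that results "positive as well as inconclusive and negative will be published in the same public accessible database".
- Late wording would secure little. The plan is dated 1 December 2020, section 6.5 puts last enrolment at about November and last completion at about December 2020, the study is open-label, and sections 8.1 and 10.2 allow real-time data review. A study-level rule added just before database lock could follow sight of most answers.

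**Conclusion.** No change is needed. This is a gap in detail that an analyst fills sensibly from the plan itself. The main conclusion rests on comfort because it is the sole primary objective and endpoint. Every test is unadjusted because section 9.1 sets one level and one confidence coefficient for all endpoints. The clash between sections 3.2 and 9.1 is a drafting inconsistency that alters no test, cut-off or result.

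The exact figures are 15/20 to pass and a 2.07% error per claim, given 20 evaluable answers. The chance of at least one false pass among 22, about 12% to 30% (37% if independent), rests on every true rate being exactly 50% and on assumed correlations. It bears on a study-level pass only under an any-claim reading that the plan does not state. Leaving the secondary claims unadjusted is a fair trade-off in a 20-man exploratory study that is to publish all its results.
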